1.0 Objective and Specific Aims

The purpose of the Inhibitor Eradication Trial is to eradicate inhibitor formation in children and adults with severe hemophilia A. This 48-week phase III open-label, randomized, controlled trial, comparing *Eloctate* immune tolerance induction (ITI) plus the bispecific monoclonal antibody FVIII mimic, Emicizumab, vs. Eloctate ITI alone, to eradicate inhibitor formation in children and adults with severe hemophilia A, including those developing inhibitors in the Prevention Trial or those ITI-refractory or ITI-naïve never-tolerized inhibitors at the same HTCs. In this trial, time to inhibitor eradication with Eloctate ITI plus Emicizumab vs. Eloctate ITI will be assessed in the eradication of inhibitor formation in children and adults with severe hemophilia A and current or past high-responding inhibitors, defined as anti-FVIII > 5.0 B.U. The research in this trial is considered greater than minimal risk as it involves combining agents to eradicate inhibitors and obtaining special inhibitor studies. The primary endpoint will be the probability of inhibitor eradication by 48 weeks, defined as anti-FVIII < 0.6 B.U. by chromogenic Nijmegen Bethesda assay (CBA), repeated immediately and confirmed within 4 weeks. Secondary endpoints will include a) safety, measured by frequency of bleeds (hematomas, joint, CNS bleeds) and b) mechanism of inhibitor eradication, measured by FVIII-specific T cell ELISPOT assay, performed on peripheral blood mononuclear cells (PBMCs) at baseline and at 4, 12, 24, 36, and 48 weeks. The B cell, Ig, and RNA assays and cytokine assays will be performed on an aliquot of PBMCs to determine the role of T regs in eradication of immune response to FVIII. Studies will be performed on T cell populations depleted of regulatory T cells (T reg) (CD4+CD25+FoxP3+) to determine the role of T regs in controlling immune response to FVIII. Hemophilia genotype and HLA assays will be determined at baseline on the buffy coat of plasma. A microbiome (stool sample) will be obtained at baseline. The trial will assess inhibitor eradication after each subject completes the 48-week trial. The Inhibitor Eradication Trial is designed to test whether Eloctate ITI plus Emicizumab is superior to Eloctate ITI alone in inhibitor eradication by 48 weeks. At the interim, once 75% of the subjects are randomized, the Bayesian posterior probability that either arm, Eloctate ITI plus Emicizumab or Eloctate ITI alone, is more likely to be inhibitor-free must be at least 99.5% to stop the trial. Assuming that the trial does not stop at the interim to declare superiority at the end of the trial, the Bayesian posterior probability that either arm, *Eloctate ITI plus Emicizumab* or *Eloctate ITI* alone, is more likely to be inhibitor-free must be at least 97.9%. This maintains the type 1 error at 5% with at least 80% power for superiority if we assume that the true condition is that Eloctate ITI plus Emicizumab is 15% superior to Eloctate ITI alone (95% vs 80% inhibitor-free).

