Equipoise: We are in a state of equipoise as the optimal approach to eradicate inhibitors in hemophilia is not known. While a randomized trial established that 200 IU/kg daily has been adopted as the standard of care for immune tolerance induction (ITI). However, only 70-80% respond, and ITI is time intensive, burdensome, taking up to 9-12 months with some requiring ports and lines, and costly. Further, those not tolerized within the first year of inhibitor onset are often refractory to ITI. Thus, simpler, more effective approaches to eradicate inhibitors is critical to improve outcomes. With the availability of Eloctate, small studies of ITI using 100 IU/kg every other day has reduced time to inhibitor eradication by nearly 50%, but these studies were not randomized. Among the reasons time to ITI eradication is long is the problem of breakthrough bleeds, which may activate the immune system "danger", and thus, use of Emicizumab by promoting hemostasis and avoiding factor VIII, could potentially reduce bleeds during ITI and reduce time to ITI. However, no data exist on whether Emicizumab reduces time to ITI. However, if breakthrough bleeds occur on Emicizumab, the requirement for FVIII to treat these bleeds could negate the potential effect of Emicizumab on ITI could be lost. In small nonrandomized studies, Emicizuab have indicated it is safe in infants but there are no data and no randomized trials to determine who might benefit or the optimal dose and/or combination of these agents to shorten ITI.

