Laboratory Specimens. A 3.8 ml (¾ tsp) blood sample, including a citrate (plasma) tube and a heparin (PBMC) tube will be drawn on all subjects at baseline, week 4, 12, 24, 36, and 48 of the trial. All samples will be drawn before administration of the study drug(s). All assays in the study are validated for small pediatric volumes, so total blood draw is 22.8 ml (4½ tsp) over the 48-week study for the anti-FVIII by chromogenic Nijmegen-modified Bethesda (CBA) assay, FVIII-specific T cell ELISPOT assay, trough FVIII (chromogenic assay), HLA, hemophilia genotype, and sample for storage (See Appendix, Table). De-identified plasma (citrate) blood samples will be processed, frozen, and shipped to a repository under the direction of [name], Coagulation Laboratory, Vitalant, Pittsburgh PA. The inhibitor (anti-FVIII) by chromogenic Nijmegen Bethesda assay (CBA) will be run real time on citrate plasma samples, with confirmation on stored aliquots for those testing positive (anti-FVIII > 0.6 B.U.). The hemophilia genotype and HLA type will be performed on buffy coat from the citrate sample at baseline only, and the FVIII trough by chromogenic assay will be run on an aliquot of the citrate sample. Samples for future testing will be stored up to 5 years after the end of the study. De-identified heparinized samples (PBMC) will be sent to the laboratory of [name], Uniformed Services University of the Health Sciences (USUHS), Bethesda, MD. The PBMC sample will be snap frozen in dimethyl sulfoxide (DMSO) and stored in liquid nitrogen until batch testing for FVIII-specific T cell responses by ELISPOT assay. Samples for future testing (hemophilia genetic and immunology studies) will be stored indefinitely after the end of the study. Any part of subject blood samples that remains after the planned blood tests are done will either be destroyed or all identifiers and means of linking it back to the subject will be permanently removed prior to sending to repository for storage. The remaining sample will be used only for genetic and immunologic studies related to inhibitor development and hemophilia. The stool sample will be collected by patients at home, placed in a tube, and returned in a container to Vitalant, and transported locally to VMI, Pittsburgh PA.

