The **Primary Endpoint** is the probability of becoming inhibitor-free by 48 weeks, where the eradication of inhibitor formation is defined as anti-FVIII < 0.6 B.U. by chromogenic Nijmegen Bethesda assay (CBA). We *hypothesize* that tolerance induction with *Eloctate ITI* plus *Emicizumab* is superior to *Eloctate ITI* alone in eradicating inhibitors in children and adults with severe hemophilia A and inhibitors. While both drugs may shorten ITI and even be synergistic, there is equipoise.

Analysis of the Primary Endpoint: We propose to take advantage of prior historical information on inhibitor formation to improve power on the Prevention Trial, and efficient use of inhibitors developing on the Prevention Trial (PRO19040140) to enroll in the Eradication Trial. For the **Eradication Trial**, we propose a Bayesian design and analysis plan to test if *Eloctate* ITI plus *Emicizumab* is superior to *Eloctate ITI* alone. Given the lack of data on either arm, we used two non-informative priors and 1:1 randomization allocation. Non-informative Bayesian priors were used for both arms as there are no published data regarding the time to inhibitor eradication with *Emicizumab* or Eloctate. The time to inhibitor eradication will be compared between the two assigned treatment arms by piecewise exponential survival models to determine the probability of being inhibitor-free at 48 weeks. Monte-Carol Markov-Chains (MCMC) were utilized to determine the posterior probability of the outcome when determining the operating characteristics. At the interim, once 75% of the subjects are randomized, the Bayesian posterior probability that either *Eloctate ITI plus Emicizumab* or *Eloctate ITI alone* is more likely to be inhibitor-free must be at least 99.5% to stop the trial. Assuming the trial did not stop at the interim, then to declare significance at the end of the trial, the Bayesian posterior probability that either arm, *Eloctate ITI*

plus Emicizumab or *Eloctate ITI alone* is more likely to be inhibitor-free at must be 97.9%. This maintains type 1 error at 5%, two-sided, with at least 80% power for superiority if we assume the true condition is that *Eloctate ITI plus Emicizumab* has an inhibitor-free rate of 95% and Eloctate ITI has an inhibitor-free rate of 80%.

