APPENDIX Schedule of Events

Table Study Week	Schedule of Events												
	Week 0	Week 4	Week 8	Week 12	Week 16	Week 20	Week 24	Week 28	Week 32	Week 36	Week 40	Week 44	Week 48
Study Visit	1	2	3	4	5	6	7	8	9	10	11	12	13
Screening, consent	Х												
Initiate study arms	Х												
Initiate study diary	X												
Clinical monitoring		Х	Х	Х	Х	Х	Х	Х	Х	Х	Х	Х	Х
End-of-study visit													Х
Laboratory tests													
Anti-FVIII NBU chromogenic	Х	Х		Х			Х			Х			Х
Hemophilia genotype*	Х												
HLA type*	Х												
FVIII chromogenic (trough)*	X	Х		Х			Х			Х			Х
T cell (ELISPOT, Ig, RNA)**	X	Х		X**			X**			Х			Х
Microbiome	Х												
Sample for storage	Х	Х		X			Х			Х			Х

*Genotype, HLA are on buffy coat; **FVIII chromogenic is on aliquot of anti-FVIII; **ELISPOT is after 5 exposure days, in lieu of wk 12 or 24, if closer.

Summary of changes to 08-08-20 protocol (clarification) Protocol v1.0

- 1. Page 12. Study population: clarified exclusion: surgery anticipated in the next 48 weeks (except port placement)
- 2. Page 15. Exclusion criteria: clarified exclusion: surgery anticipated in the next 48 weeks (except port placement)

Summary of changes to 10-05-20 protocol (clarification) Protocol v1.0

- 1. Page 12. Study population: clarified exclusion: if current use of Emicizumab, known start date
- 2. Page 15. Exclusion criteria: if current use of Emicizumab, known start date

Summary of changes to 10-05-20 protocol (clarification)

Protocol v2.0

- 1. Minor corrections and clarifications throughout protocol
- 2. Adaptive design updated to Bayesian platform design throughout protocol
- 3. Page 1. Protocol Version and date updated
- 4. Page 2. Endpoints: updated to include microbiome stool sample
- 5. Page 4. Objective and Specific Aims: Addition of microbiome stool sample
- 6. Page 6. Specific Aim 2: Addition of microbiome stool sample
- 7. Page 6. Specific Aim 1 and 2: Clerical correction; Emicizumab and corrected to Eloctate
- 8. Page 8. Screening Period: Addition of microbiome stool sample
- 9. Page 12. Study population: clarified exclusion: if current use of *Emicizumab*, known start date
- 10. Page 15. Exclusion criteria: if current use of Emicizumab, known start date

Summary of changes to 02-26-21 protocol (clarification)

Protocol v3.0

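### Section 3.6 leaves the primary survival model open: the most favourable readings give about 76–78% power and separate hazards per arm about 60–70%, against a stated 80%

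*Combined protocol and SAP*

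**What the plan says.** Section 3.5 sets N = 90. Section 3.6 assumes that the combination arm "has an inhibitor-free rate of 95% and Eloctate ITI has an inhibitor-free rate of 80" per cent. Time to eradication "will be compared between the two assigned treatment arms by piecewise exponential survival models to determine the probability of being inhibitor-free at 48 weeks". On priors and allocation it says "Given the lack of data on either arm, we used two non-informative priors and 1:1 randomization allocation", and again "Non-informative Bayesian priors were used for both arms". One interim look takes place when 75% are randomised, with a 99.5% posterior probability needed to stop; the final rule is 97.9%. Section 1.0 concludes: "This maintains the type 1 error at 5% with at least 80% power for superiority", and section 3.6 repeats this as two-sided.

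Section 3.3 says that blood samples "will be drawn on all subjects at baseline, week 4, 12, 24, 36, and 48 of the trial". The row "Anti-FVIII NBU chromogenic" in the Appendix Schedule of Events shows the same six time points.

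The document does not give the number or position of the cut points, the numeric priors, whether the arms share a baseline hazard with one hazard ratio or have separate hazards, or how an eradication that happened between two samples enters the likelihood.

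**The concern.** The two thresholds are given to three digits, but they control error and deliver power only for the model they were tuned on, and that model is not written down. The missing choices matter at this sample size. With a separate set of piecewise hazards per arm, the 48-week probability depends on late intervals that hold few subjects. With titres taken up to 12 weeks apart, the observed date is a detection date. Treating it as the event time rounds every time upwards and changes both error rates. At stake is whether the stated operating characteristics describe the analysis that will be run in this open-label trial.

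**Working it through.** **Inputs.** 45 per arm (90, 1:1); 95% vs 80% eradicated by week 48; interim at 0.75 × 90 = 67.5, so 68 randomised; thresholds 0.995 and 0.979; titres at weeks 4, 12, 24, 36 and 48 after baseline; accrual over 6 years (sections 3.3, 3.5, 3.6). Assumed because the document does not say: uniform accrual, no dropout, constant true hazards, and the priors named below.

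**Reproducing the plan's figure.** With constant hazards, HR = ln(0.05)/ln(0.20) = 2.996/1.609 = 1.861. Expected events = 45 × 0.95 + 45 × 0.80 = 78.75. By Schoenfeld, √78.75/2 × ln(1.861) = 4.437 × 0.621 = 2.756.
- At z = 1.96: Φ(2.756 − 1.96) = 78.7%.
- At the 97.9% rule (z = 2.03): Φ(2.756 − 2.03) = about 76.5%.

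So the claim is nearly reproduced. It relies on the event-time information. For the 48-week proportions alone, pooled p = 0.875, null SE = √(2 × 0.875 × 0.125/45) = 0.0697, alternative SE = √((0.16 + 0.0475)/45) = 0.0679, and power = Φ((0.15 − 1.96 × 0.0697)/0.0679) = Φ(0.197) = 58%.

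**Why separate hazards cost power.** Expected numbers still at risk at week 36 are 45 × 0.05^0.75 = 4.8 (combination) and 45 × 0.20^0.75 = 13.5 (control). Expected events in weeks 36–48 are 4.8 − 2.25 = about 2.5 and 13.5 − 9 = 4.5. With its own hazard in each interval, an arm's 48-week probability inherits the noise of these few events.

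**Simulation.** Main cases use both looks and 4,000 trials (Monte Carlo SE up to 0.8 points). Priors: Gamma with shape 0.001 or 0.01 (vague) or 0.5 (Jeffreys-type) on hazards; vague to flat Beta on interval risks in the interval-censored separate model; Normal(0, SD 10) on the log hazard ratio. Ranges cover repeated independent runs.

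| Event times | Hazard structure | Power, 80 vs 95% | Type I error, 80 vs 80% |
|---|---|---|---|
| Exact | One constant hazard per arm | 76–78% | about 5% |
| Exact | Common hazard ratio | 77% | about 4–5% |
| Exact | Separate, one cut at week 24 | 64–66% | about 4–5% |
| Exact | Separate, 4 or 5 intervals | 61–67% | about 5–6% |
| Interval-censored | One constant hazard per arm | 77% | 4.6% |
| Interval-censored | Common hazard ratio | 76–77% | about 4–5% |
| Interval-censored | Separate, cuts at visits | 63–67% | 5.1–6.0% |
| Visit date as exact | One constant hazard per arm | 61–63% | about 2% |
| Visit date as exact | Common hazard ratio | 58% | 1–2% |
| Visit date as exact | Separate, 2 to 5 intervals | 34–50%, by prior | 1–2% |

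The 63% in the interval-censored separate row is from the final look only. A more informative Gamma(1) prior gives 69–71% for separate hazards in 2 to 5 intervals with exact times. In the last row, vague priors with 4 or 5 intervals give 34–37% and Gamma(1) about 50%.

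**How much of the visit-date loss is miscalibration.** With the threshold reset to 5% type I error (final look only, 2,500 trials), five separate intervals rise from 35% to 56% (vague) or from 42% to 62% (Gamma(0.5)). One hazard per arm rises from 62% to 78%.

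**The case against.** The sponsor can answer that section 3.6 reports MCMC operating characteristics, so some model was simulated, and that one constant hazard per arm comes within 2–3 points of the claim at close to 5% type I error. Non-informative priors for both arms fit that reading as well as they fit separate piecewise hazards; the wording does not decide between them. Sections 3.2 and 3.6 also let a local laboratory result start the endpoint, so not every date need fall on the central schedule. All of this stands. It shows that a model close to the claim exists, but not which model will be run. A local result is still a detection date bounded below by the last positive sample.

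Four stronger readings are tempting, and the documents do not support them.
- A reader might infer that N = 90 has only about one-third power. That needs visit dates as exact times, vague priors and an untouched threshold together. Its type I error of 1–2% conflicts with the 5% that section 3.6 says was maintained.
- A reader might infer that separate hazards can never come near 80%. Twelve 4-week intervals with Gamma(1) priors reach 80%. That result is driven by the prior: with Gamma(0.5) the same cuts give 75% at 7.1% type I error.
- A reader might infer that type I error is inflated by picking whichever model passes. Nothing in the plan provides for such a choice.
- A reader might infer that a common hazard ratio must be the primary model. That is a trade-off. In one assumed case, both arms reach 80% by week 48 but control is slower early (Weibull shape 1.5 vs 1.0). There the common ratio declares a difference in 11.5% of trials, against 7.4% with separate hazards.

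**Conclusion.** The point holds as a specification gap with a measurable effect on power. Under constant true hazards, no dropout and vague or Jeffreys-type priors, the most favourable readings give about 76–78%, just short of the statement, and separate piecewise hazards give about 60–70%. A fit that takes visit dates as exact times has neither the stated error rate nor the stated power at 97.9%: type I error is about 1–2%, with power about 61–63% for one hazard per arm and about 34–50% for separate hazards, part of which a reset threshold would recover.

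The one-hazard figure also depends on the hazard being truly constant. With exact times and Weibull shapes 0.7, 1.5 and 2 it becomes 88%, 59% and 41%, while five separate intervals give 69%, 65% and 62%. The claim could therefore be met if hazards fall over time. None of this proves the sponsor's simulation wrong, since its model is not shown. It is something to correct before the interim.

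**What to change.** In section 3.6, before the 75% interim:

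1. Use a piecewise exponential model with cut points at weeks 4, 12, 24 and 36 and an interval-censored likelihood between anti-FVIII visits.
2. State the hazard structure and numeric priors that were used to set the 99.5% and 97.9% thresholds, and name the alternative structure as a sensitivity analysis.
3. Re-run type I error and power for exactly that model on the visit schedule. Reset the threshold if type I error is not 5%. Replace the 80% power statement, there and in section 1.0, by the simulated value: about 77% for one hazard per arm or a common ratio, about 60–70% for separate hazards.

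The cost is a paragraph, a re-run of the simulation and a slightly less favourable stated power. No patients, visits or assays are added.

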4.0 Human Subjects

4.1 General Characteristics - Minority Inclusion and Non-Discriminatory Statements

For the Inhibitor Eradication Trial, adults or children \geq 4 months of age with severe hemophilia A and a current or past high-responding inhibitor to FVIII, anti-FVIII \geq 5.0 B.U., are eligible to participate. Subjects will include those who develop inhibitors in the Prevention Trial or those who have been refractory or never tolerized at the same HTCs. As hemophilia is an X-linked congenital disorder, >98% of whom are male, it is anticipated that the study population will be male, and as almost 90% are Caucasian, it is anticipated that the majority of subjects will be Caucasian males. For the trial, subjects will be children or adults \geq 4 months of age with severe hemophilia A, FVIII < 0.01 IU/mI), with current or past high-responding inhibitor to FVIII, anti-FVIII \geq 5.0 B.U.

Currently there is no known effective approach to eradicate inhibitors, and they remain major complications of hemophilia. The trial will assess *Eloctate* ITI (tolerance induction) with or without *Emicizumab* to eradicate inhibitors, and rFVIIa will be used to treat bleeds. There will be no discrimination based on race or ethnicity (see Targeted/Planned Enrollment Table). The racial, gender and ethnic characteristics of the proposed subject population reflects the demographics of Pittsburgh, surrounding area, and the subject population of the University of Pittsburgh Medical Center. We shall attempt to recruit subjects in proportion to these demographics. All subjects will be screened prior to enrollment to confirm the diagnosis of severe hemophilia A, FVIII < 0.01 U/ml. Written, informed consent will be obtained from all subjects at the screening visit. Once eligibility is confirmed, visit 1 will be the start of enrollment. For the Eradicate Trial, 90 subjects (2-4 per site) will be enrolled.

4.2 Inclusion of Children:

The optimal approach to prevention and eradication of inhibitor formation in hemophilia is unknown. Among those

who develop inhibitors, 95% occur within 50 treatment exposures, usually in the first two years of life, but unless inhibitors are tolerized, they may last a lifetime, and thus affect children and adults of all age. Thus, the **Inhibitor Eradication Trial** is limited to male children or adults with severe hemophilia A and an inhibitor to factor VIII, anti-FVIII \geq 5.0 B.U.

4.3 Inclusion/Exclusion Criteria

Inclusion criteria:

- 1. Children or adults \geq 4 months of age.
- 2. Severe hemophilia A, FVIII < 0.01 U/ml.

Exclusion criteria:

Subjects will be excluded from study entry if any of the following exclusion criteria exist:

- 1. Acquired hemophilia or any bleeding disorder other than hemophilia A.
- 2. Unwilling to discontinue pre-trial *Emicizumab* before randomization.
- 3. Use of an experimental drug(s).
- 4. Surgery anticipated in the next 48 weeks (except port placement).
- 5. Life expectancy less than 5 years.
- 6. Patient/parent/caretaker unable or unwilling to keep a personal diary of bleeding frequency and study drug treatment, make monthly visits and blood draws.
- 7. Other illness, condition, or reason in the opinion of the investigator that would make the patient unsuitable for the trial.

4.4 Recruitment Procedures

It is anticipated that 2-4 subjects will be enrolled in the Eradication Trial at this study site. Patients or parents/caretakers of children with a diagnosis of severe hemophilia A and inhibitors will be approached for participation in the trial. Patients or parents will specifically be contacted during routine clinic visits to determine if they or their child are interested in participating in the study. There will be no cold-calling. The study physicians, as their clinical care doctors, see FVIII-deficient children at routine clinic visits and will determine the patient or parent/caretaker interest in study participation. If they are interested, the study physicians will discuss the study in further detail and review the informed consent. Each and every potential patient or parent/caretaker will discuss the study with their study physicians and will be encouraged to take time to decide on participation and ask questions. If a patient or parent/caretaker decides to take a consent form home for further viewing, they may contact a study nurse if they wish to participate, at which time; they will be scheduled again to visit/discuss/review consent with study physicians for enrollment. Discussion will include the purpose, safety issues, and risks and benefits of the study. The study physicians will answer any questions and will obtain the consent. No experimental procedures or interventions will occur until after informed consent is obtained. The investigator's certification statement will be signed at the time consent is obtained. If any new information occurs during the conduct of the study, the patient or the parent/caretaker who has provided consent will be informed and will be reconsented with this information at the next visit. A de-identified prescreening/screening log will be kept, and all reasons for exclusion documented in study source documents and screening log. Patients or parent/caretakers who read the consent form are free to refuse enrollment, and they will be free to withdraw their or their child's consent at any time. If patients or parents/caretakers wish to withdraw consent, they may do so by addressing a letter to the principal investigator.

Any data collected or blood samples drawn prior to the time of withdrawal will continue to be used, but no additional information or blood samples will be collected. Processed blood sample results will continue to be used for the research study; however, remaining samples will be destroyed or used as indicated by the patient or parent/caretaker's letter. The reason (e.g. AE, lost to follow-up, etc.) and date of withdrawal for all subjects withdrawn from this study will be recorded. Subject information will be captured and managed by study sites on electronic CRFs via the INHIBIT Trial DCC Data Management System. The sIRB may inspect the records of this study. Every effort will be made to keep the subject's personal medical data confidential.

Subject eligibility for the study will be determined after screening. Subjects are to use their own supply of *Eloctate* or *Emicizumab* during the study. The patients or parents/caretakers will sign informed consent and baseline labs will be

drawn, including anti-FVIII level, FVIII-specific T cell assays (ELISPOT), FVIII trough level, hemophilia genotype and HLA type. Subject enrollment and screening will be conducted by the local Investigator, in communication with the INHIBIT Trial DCC Data Management System. Subjects will be considered enrolled in the study after all assessments have been completed during the Screening period and just prior to *Eloctate or Emicizumab* administration. No subject may begin treatment prior to enrollment and assignment of a unique subject identification number. Any subject identification numbers that are assigned will not be reused even if the subject does not receive treatment.

Demographic Chart: Targeted Enrollment for Study

TARGETED/PLANNED ENROLLMENT: Number of Subjects								
Ethnic Category		Sex/Gender						
Ethnic Category	Females	Males	Total					
Hispanic or Latino	0	3	3					
Not Hispanic or Latino	0	87	87					
Ethnic Category: Total of All Subjects *	0	90	90					
Racial Categories								
American Indian/Alaska Native	0	0	0					
Asian	0	4	4					
Native Hawaiian or Other Pacific Islander	0	0	0					
Black or African American	0	8	8					
White	0	78	78					
Racial Categories: Total of All Subjects *	0	90	90					

* The "Ethnic Category: Total of All Subjects" must be equal to the "Racial Categories: Total of All Subjects."

Subjects are only enrolled after the Investigator has verified that they are eligible. Subjects withdrawn from the study after enrollment and prior to receiving *Eloctate with/without Emicizumab* will be replaced. A subject eligibility form will be provided for the Investigator to verify that the Inclusion and Exclusion Criteria have been satisfied for each subject. The site (HTC) coordinator will upload the screening information to the INHIBIT Trial DCC Data Management System. Following confirmation of the subject's eligibility along with the subject identification number, an accession number will be generated in the database. Once the subject identification number has been assigned, the subject may be randomized and then initiate the assigned treatment, *Eloctate with/without Emicizumab*, preferably in the morning.

